5.2.1 Dose Selection/Modification

5.2.1.1 Dose Selection

The rationale for selection of doses to be used in this trial is provided in Section 4.0 - Background and Rationale.

The dose of pembrolizumab is fixed at 200 mg IV Q3W.

The dose escalation schema of trametinib is as follows. Each cycle is Q3W (21 days).

Table 3. Dose Escalation Schema for Trametinib

Dose Level	Trametinib dose (PO Daily) Q3W	Pembrolizumab (MK-3475) dose IV Q3W
-1	1.5 mg (D1-D7)	200 mg
*1	1.5 mg (D1-D10)	200 mg
2	2.0 mg (D1-D10)	200 mg

^{*} Dose level 1 is the starting dose. For each cohort, trametinib dose will be the same for lead in and for concurrent trametinib + pembrolizumab administration.

For Cohort A: Lead in trametinib will precede combination trametinib and pembrolizumab, which will commence for C2.

For Cohort B: Lead in pembrolizumab will precede combination trametinib and pembrolizumab, which will commence for C2.

The recommended dose expansion and recommended phase II dose (RP2D) will be determined by the overall assessment of the MTD (the maximum dose level where 6 patients have been treated in the dose escalation portion of the study) and toxicities observed in the dose escalation portion of this study.

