Grade 1*	Consult ophthalmologist within 7 days of onset.	 If dilated fundus examination cannot be performed within 7 days of onset, hold trametinib until RPED and RVO can be excluded by retina specialist/ophthalmologist. If RPED and RVO excluded, continue/or restart trametinib at same dose level. If RPED suspected/diagnosed: See RPED dose modification table below (following this table); report as SAE. If RVO diagnosed: Permanently discontinue trametinib and report as SAE.
Grade 2 and Grade 3	Consult ophthalmologist immediately.	 Hold trametinib If RPED or RVO excluded, restart trametinib at same dose level after visual AE is ≤ grade 1. If no recovery within 3 weeks, discontinue trametinib If RPED diagnosed: See RPED dose modification table below; report as SAE. If RVO: Permanently discontinue trametinib and report as SAE.
Grade 4	 Consult ophthalmologist immediately. Report as SAE. 	 Hold Trametinib If RPED/RVO excluded, may restart trametinib at same or reduced dose after discussion with the Principal Investigator If RVO or RPED, permanently discontinue trametinib.

Abbreviations: RPED=retinal pigment epithelial detachments; RVO=retinal vein occlusion; SAE=serious adverse event

* If visual changes are clearly unrelated to study treatment (e.g., allergic conjunctivitis), monitor closely but ophthalmic examination is notrequired.

Table 11. Trametinib Dose Modification for RPED

Event CTCAE Grade	Action and Dose Modification
Grade 1 RPED (Asymptomatic; clinical or diagnostic observations only)	Continue treatment with retinal evaluation monthly until resolution. If RPED worsens, follow instructions below.
Grade 2-3 RPED (Symptomatic with mild to moderate decrease in visual acuity; limiting instrumental ADL)	 Interrupt trametinib. Retinal evaluation monthly. If improved to ≤ Grade 1, restart trametinib with one dose level reduction (reduced by 0.5 mg) or discontinue in patients taking trametinib 1 mg daily. If no recovery within 4 weeks permanently discontinue trametinib

Table 12. Management and Dose Modification Guidelines for Diarrhea

CTCAE Grade	Adverse Event Management	Action and Dose Modification

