Grade 1	 CT scan (high-resolution with lung windows) recommended. Work-up for infection. Monitoring of oxygenation via pulse- oximetry recommended. Consultation with pulmonologist recommended. 	Continue trametinib at current dose.
Grade 2	 CT scan (high-resolution with lung windows). Work-up for infection. Consult pulmonologist. Pulmonary function tests: If < normal, repeat every 8 weeks until ≥ normal. Bronchoscopy with biopsy and/or BAL recommended. Symptomatic therapy including corticosteroids if clinically indicated. 	 Interrupt trametinib and pembrolizumab until recovery to grade ≤1. If AE resolved to Grade ≤1 and relationship to trametinib and or pembrolizumab is equivocal, restarting pembrolizumab and trametinib (with dose reduction at investigators discretion) may be considered, after discussion with the study chair. If treatment delay is > 4 weeks, permanently discontinue trametinib and pembrolizumab.
Grade 3	 CT scan (high-resolution with lung windows). Work-up for infection. Consult pulmonologist. Pulmonary function tests-if < normal, repeat every 8 weeks until ≥ normal. Bronchoscopy with biopsy and/or BAL if possible. Symptomatic therapy including corticosteroids as clinically indicated. 	Permanently discontinue trametinib and pembrolizumab.
Grade 4	• Same as grade 3.	Permanently discontinue trametinib and pembrolizumab.

Dose Reduction Scheme for Trametinib

No dose reductions for trametinib are permitted below 1.5 mg PO daily.

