5.4 Definition of Dose Limiting Toxicities

All toxicities will be graded using National Cancer Institute (NCI) CTCAE Version 4.0. The occurrence of any of the following toxicities during the first two cycles (i.e. after completion of the lead in cycle and the first cycle where both pembrolizumab and trametinib are administered) will be considered a DLT, if judged by the Investigator to be possibly, probably or definitely related to study drug administration. The goal of the dose escalation portion of the study is to assess the safety of the combination after pembrolizumab or trametinib lead in, therefore, patients must have completed the lead in phase and also have received both trametinib and pembrolizumab concurrently to be evaluable for a DLT.

A DLT evaluable subject is defined as a subject who receives treatment for the 6 week dose-limiting toxicity (DLT) observation period and who receives at least 80% of all planned treatments. A subject who does not receive at least 80% of planned treatment due to AEs that are unrelated to study treatment will not be considered evaluable for DLTs and may be replaced as

needed during dose escalation or dose confirmation. More than 3 or 6 subjects may be enrolled to a given dose level if needed to replace subjects who are not evaluable for DLT or to ensure a thorough evaluation of a given dose level during the dose escalation part of the study. An event will be considered a dose-limiting toxicity (DLT) if it occurs during the first two cycles of treatment (first 6 weeks after initiating treatment) and meets at least one of the following criteria:

- Clinically significant hematologic toxicity (e.g. grade 4 neutropenia lasting more than 7 days or accompanied by neutropenic fever, or Grade 4 thrombocytopenia of any duration)
- Clinically significant Grade ≥3 non-hematologic toxicity that has not been previously identified for either pembrolizumab or dabrafenib/trametinib and cannot be controlled with routine supportive measures (e.g. anti-emetics)
- Clinically significant Grade ≥3 non-hematologic toxicities that are known to occur with either pembrolizumab or trametinib but that cannot be controlled using the recommended product-specific supportive measures (e.g. steroids for pembrolizumab -related immune toxicities)

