- Drug-related toxicity, regardless of CTCAE grade, that results in an interruption of any component of study therapy during Cycle 1 for more than 21 consecutive days and cannot be controlled within 2 weeks from its onset
- Any other Grade 2 or greater non-hematological toxicity that in the judgment of the investigator and Sponsor Investigator is dose limiting, with the exception of mild or moderate immune -mediated adverse reactions or symptomatic endocrinopathy attributable to pembrolizumab
- For Liver Function Tests
 - ALT or AST $\geq 8x$ ULN
 - ALT or AST \geq 5x ULN but \leq 8x ULN persists for \geq 2 weeks
 - ALT or AST ≥3x ULN if associated with the appearance or worsening of symptoms of hepatitis or hypersensitivity such as fatigue, nausea, vomiting, right upper quadrant pain or tenderness, pyrexia, rash or eosinophilia.

The following will NOT be considered a DLT for the purposes of this protocol:

• Clinically insignificant laboratory values of any grade (i.e. asymptomatic amylase, lipase elevations).

Dose escalation will proceed within each cohort according to the following scheme. Dose-limiting toxicity (DLT) is defined above.

The MTD is the highest dose tested in which ≤ 1 out of 6 patients has experienced a DLT.

Table 15: Dose Escalation Decision Rule Summary

Number of Patients with DLT at a Given Dose Level	Escalation Decision Rule
0 out of 3	Enter 3 patients at the next dose level.
≥2	Dose escalation will be stopped. This dose level will be declared the maximum administered dose (highest dose administered). Three (3) additional patients will be entered at the next lowest dose level if only 3 patients were treated previously at that dose.
1 out of 3	 Enter at least 3 more patients at this dose level. If 0 of these 3 patients experience DLT, proceed to the next dose level. If 1 or more of this group suffer DLT, then dose escalation is stopped, and this dose is declared the maximally administered dose. Three (3) additional patients will be entered at the next lowest dose level if only 3 patients were treated previously at that dose.
≤1 out of 6 at highest dose level below the maximum administered dose (unless ≤1 out of 6 patients have DLT's at Dose Level 2 – in which case this is also the MTD).	This is the maximum tolerated dose (MTD), and generally the recommended phase 2 dose (RP2D). At least 6 patients must be entered at the RP2D.

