8.0 STATISTICAL ANALYSIS PLAN

The initial dose escalation will follow a standard 3+3 design, starting at dose level 1. The decision to escalate to the next dose level will be determined by the rate of dose-limiting toxicity (DLT) observed during Cycle 2, with a cycle length defined as 3 weeks. Up to 3 patients will be initially enrolled in a dose cohort, starting at dose level 1. If 1 of 3 patients were to experience DLT, 3 additional patients will be enrolled at same dose level. If 0 of 3 patients or 1 of 6 patients enrolled at a dose level were to experience DLT, enrollment to next dose level will be opened. If >1 of 3 patients or >1 of 6 patients enrolled at a dose level were to experience DLT, the maximum tolerated dose (MTD) will have been exceeded. Adverse events will be collected and described for the expansion cohorts. Enrollment to dose level 1 will be expanded to 6 patients if applicable, or enrollment to dose level -1 will be opened if dose level 1 were to exceed the MTD. The highest dose level at which 0 of 3 patients or 1 of 6 patients experience DLT will be declared the MTD. A minimum of 6 patients and maximum of 18 patients will be enrolled for each cohort (Arm A: Lead in Trametinib and Arm B: Lead in Pembrolizumab) in this dose escalation portion of the study.

Enrollment into Cohorts A and B are pre-planned in regards to sequence and timing. Arm A (lead in trametinib) will open 1st to dose escalation and will accrue 3 patients. Once 3 patients are accrued for Arm A, Arm B will open and accrue 3 patients. This is to ensure cohorts remain open for accrual given the 6-week DLT period; these cohorts will alternate in opening in this fashion until the MTD is achieved for both Arm A and Arm B. Once the MTD is achieved for both Arms A and B, Arm A will open to dose expansion at the MTD and complete accrual, followed by Arm B. If one Arm is delayed in opening additional dose levels due to toxicity, the alternate cohort may open at additional dose levels if approved by the Primary Investigator in consultation with Novartis and Merck.

The recommended dose expansion and recommended phase II dose (RP2D) will be determined by the overall assessment of the MTD and toxicities observed in the study.

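### Section 5.4 need not count a table-mandated loss of a drug to related toxicity as a DLT, and its interruption and 80% evaluability rules fit neither the 6-week window nor the SAP

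*Combined protocol and SAP*

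**What the plan says.** **DLT criteria (Section 5.4).** An event is a DLT "if it occurs during the first two cycles of treatment (first 6 weeks after initiating treatment") and if it meets a listed criterion. Three criteria matter here.

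- Grade 3 or higher non-hematologic toxicities "known to occur with either pembrolizumab or trametinib but that cannot be controlled using the recommended product-specific supportive measures" are DLTs. Steroids are the example given of such a measure.
- Drug-related toxicity of any grade counts if it causes "an interruption of any component of study therapy during Cycle 1 for more than 21 consecutive days" and also is not controlled within 2 weeks of onset.
- Any other non-hematologic toxicity of Grade 2 or more counts if the investigator and Sponsor Investigator judge it dose limiting. Mild or moderate immune-mediated reactions and symptomatic endocrinopathy from pembrolizumab are excepted.

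**Treatment tables (Section 5.2.1.2).** For Grade 3 and Grade 4 pneumonitis, Table 14 says to "permanently discontinue trametinib and pembrolizumab", without reference to control. Table 5 ends pembrolizumab for Grade 3-4 pneumonitis, nephritis and infusion reactions. Table 10, in the row for Grade 1 visual changes, says: "If RVO diagnosed: Permanently discontinue trametinib and report as SAE".

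**Schedule (Sections 5.2 and 5.2.1.1).** "Each cycle is Q3W (21 days"). At dose levels 1 and 2, trametinib is given on Days 1-10. Cycle 1 is a single-drug lead-in in both arms, and the combination starts in Cycle 2.

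**Evaluability and replacement.** Section 5.4 defines an evaluable subject as one treated for the 6-week period and "who receives at least 80% of all planned treatments". Its next sentence makes non-evaluable only those whose shortfall comes from unrelated AEs. Section 8.0 replaces escalation subjects who leave the study and are not evaluable, and does not replace patients removed for unacceptable related AEs.

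**Escalation (Section 8.0).** The decision rests on DLTs "observed during Cycle 2, with a cycle length defined as 3 weeks". A level clears on 0 of 3 or 1 of 6.

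**The concern.** The primary objective is the safety and tolerability of the combination, and the MTD is the main output of escalation. A related toxicity that forces a patient off one or both drugs within six weeks is direct evidence about tolerability. Under the present wording that patient may be scored as DLT-free, may have no clear evaluability status, or may meet a lost-treatment criterion written for a cycle in which the combination is not given. The 3+3 responds to very few events: one patient more or fewer among six decides whether a level clears. Twelve patients per arm then enter expansion at the dose that results.

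**Working it through.** **1. The window.** 2 cycles x 21 days = 42 days = 6 weeks, which reproduces the period in Section 5.4. Section 8.0 names Cycle 2 alone for the escalation decision, yet refers in its next paragraph to a 6-week DLT period. The window therefore differs between the sections and within Section 8.0.

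**2. Mandated discontinuation against the DLT list.** Take Grade 3 pneumonitis that starts on Cycle 2 Day 12 and responds to steroids, the treatment Section 5.6.2 directs.

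- Planned administrations already given: Arm A, 10 + 10 trametinib days + 1 infusion = 21 of 21; Arm B, 2 infusions + 10 trametinib days = 12 of 12. The patient is evaluable if the 6-week period is otherwise completed.
- Table 14 ends both drugs.
- The known-toxicity criterion is not met, because supportive measures controlled the event. The interruption criterion is not met, because the event began in Cycle 2 and was controlled.
- Only the judgement criterion remains.

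This example depends neither on the 80% rule nor on how the interruption criterion is read.

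**3. The interruption criterion, on each reading.**

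- Strict, fixed 21-day Cycle 1: the longest gap is Days 1-21 = 21 days, or 20 days after a Day 1 dose. Neither exceeds 21.
- Replacing Cycle 1 with Cycle 2 would not help: Days 22-42 = 21 days, or 20 after a Cycle 2 Day 1 dose.
- Lenient, starting in Cycle 1 and running on: reachable. In Arm A, with the last trametinib dose on day d, dosing restarts on day d + 23 or later (d = 1: Day 24; d = 8: Day 31). On an undelayed calendar such a patient has received 10 or 11 of 21 planned administrations (48% or 52%), below the 80% floor. The same patient would meet the DLT criterion and fail the literal evaluability definition.
- Cycle 1 lengthened by a late Cycle 2 start: reachable, and the patient may still complete treatment.
- On every reading, an interruption that starts in Cycle 2 is outside the criterion.

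**4. The 80% threshold.** Section 5.4 does not define the unit of planned treatment. Assume each infusion and each trametinib day counts as one.

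- Arm A: 0.8 x 21 = 16.8, so 17 are needed. Trametinib stopped after Cycle 2 Day 5: 10 + 5 + 1 = 16, 76%. After Day 6: 17, 81%.
- Arm B: 0.8 x 12 = 9.6, so 10 are needed. Trametinib stopped after Cycle 2 Day 7: 2 + 7 = 9, 75%. After Day 8: 10, 83%.
- Losing only pembrolizumab after Cycle 2 Day 1 misses no planned dose in the window in either arm.

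**5. Effect on the 3+3.** With per-patient event probability p, P(clear) = (1-p)^3 + 3p(1-p)^2 x (1-p)^3.

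- p = 0.10: 0.729 + 0.243 x 0.729 = 0.906
- p = 0.20: 0.512 + 0.384 x 0.512 = 0.709
- p = 0.30: 0.343 + 0.441 x 0.343 = 0.494

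The documents give no toxicity rates, so every rate below is an assumption. The columns for further events assume that the judgement criterion captures none of them as written.

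| Listed DLT rate | Cleared as written | Further 10% counted | Further 20% counted | Further 30% counted |
|---|---|---|---|---|
| 5% | 0.973 | 0.814 | 0.600 | 0.396 |
| 10% | 0.906 | 0.709 | 0.494 | 0.309 |
| 15% | 0.814 | 0.600 | 0.396 | 0.234 |

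If 20% of patients had uncounted drug-ending events, the chance that at least 2 of 6 lose a drug without a DLT is 0.345.

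**The case against.** Excluding known, controllable toxicity from the DLT list is an explicit choice, and the plan has safeguards around it. The judgement criterion excepts only mild or moderate immune-mediated reactions; Table 20 describes Grade 3 as severe, so Grade 3 pneumonitis can be called a DLT. That judgement includes the Sponsor Investigator, which gives it a central element. Section 5.4 lets the RP2D be set below the MTD because of toxicities that are not DLTs. Section 8.0 bases the RP2D and expansion dose on overall toxicity, and Section 10.5 requires a meeting once each cohort completes DLT assessment. All of this stands. It means that such events need not count, not that they cannot. None of these safeguards carries a threshold, however, and Section 8.0 also describes expansion enrolment as at the MTD.

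A reader might infer three stronger things that the documents do not support.

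- That the interruption criterion can never be met. It can, if an interruption may start in Cycle 1 and run on, or if Cycle 1 is lengthened; the Study Calendar notes foresee longer pembrolizumab cycles.
- That patients who lose a drug usually fall below 80%. This depends on timing and on an undefined unit, and loss of pembrolizumab alone after Cycle 2 Day 1 costs no planned dose in the window.
- That the evaluability rule simply removes related shortfalls. The next sentence of Section 5.4 is limited to unrelated AEs and implies the opposite. The replacement sentence in Section 8.0 covers only those who leave the study, so a patient who continues on the other drug falls under neither of its replacement rules.

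The retinal vein occlusion example also needs care. It falls below the Grade 2 floor of the judgement criterion only if the event takes the grade of the visual change, and the documents do not say how it is graded.

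**Conclusion.** The three provisions do not line up, and a dose level can clear the 3+3 while patients lose a drug to related toxicity. Three parts are established from the text:

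- A table-mandated permanent discontinuation is not automatically a DLT.
- The only lost-treatment criterion does not fit a fixed 21-day Cycle 1, and does not cover interruptions starting in the first combination cycle, the cycle Section 8.0 names for escalation.
- The literal 80% definition conflicts with the sentence after it, and Section 8.0 does not resolve the status of related shortfalls.

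The size is not established. The fall from 0.91 to 0.71 or 0.49 shows how the 3+3 would respond at an assumed 10% listed rate, with a further assumed 10% or 20% that the judgement criterion misses. It is not an estimate for this trial. Nor do the documents show that the MTD or RP2D will be set too high, because the discretionary safeguards may catch these patients. The defect is that the plan leaves this to discretion without a threshold, although tolerability is the primary objective.

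**What to change.** 1. In Sections 5.4 and 8.0, state that a patient who misses planned treatment because of a related event stays in the DLT denominator whatever the 80% threshold gives, and is not replaced. Define the unit of planned treatment. Align Section 5.9, which lists replacement as not applicable.
2. Restate the interruption criterion so that it can be reached within the 6-week window on the intermittent schedule and covers the combination cycle. Have Sections 5.4 and 8.0 name the same DLT window. Changing the cycle number alone is not enough, since at most 21 days remain from the start of Cycle 2.
3. Reconcile Sections 5.2.1.2, 5.4 and 8.0 on whether a permanent discontinuation required by the tables for related toxicity counts as a DLT. That is a clinical choice for the sponsor; the plan needs to state it. The treatment tables need not change for this purpose.

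The cost is protocol and SAP wording, with no new data. Slightly more events or patients may count toward DLT decisions, so the MTD may be lower, or a level may need 3 more patients within the existing maximum of 18 per arm in escalation.

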5.5 Concomitant Medications/Vaccinations (allowed & prohibited)

Medications or vaccinations specifically prohibited in the exclusion criteria are not allowed during the ongoing trial. If there is a clinical indication for one of these or other medications or vaccinations specifically prohibited during the trial, discontinuation from trial therapy or vaccination may be required. The investigator should discuss any questions regarding this with the Merck Clinical team. The final decision on any supportive therapy or vaccination rests with the investigator and/or the subject's primary physician.

5.5.1 Acceptable Concomitant Medications

All treatments that the investigator considers necessary for a subject's welfare may be administered at the discretion of the investigator in keeping with the community standards of medical care. All concomitant medication will be recorded in the subject's medical record including all prescription, over-the-counter (OTC), herbal supplements, and IV medications and fluids. If changes occur during the trial period, documentation of drug dosage, frequency, route, and date may also be included in the subject's medical record.

All concomitant medications received within 28 days before the first dose of trial treatment and 30 days after the last dose of trial treatment should be recorded. Concomitant medications administered after 30 days after the last dose of trial treatment should be recorded for SAEs and ECIs as defined in Section 7.2.

5.5.2 Prohibited Concomitant Medications

Subjects are prohibited from receiving the following therapies during the Screening and Treatment Phase of this trial:

- Antineoplastic systemic chemotherapy or biological therapy
- Immunotherapy not specified in this protocol
- Chemotherapy not specified in this protocol
- Investigational agents other than pembrolizumab
- Radiation therapy
 Note: Radiation therapy to a symptomatic solitary lesion or to the brain may be allowed at the investigator's discretion.
- Live vaccines within 30 days prior to the first dose of trial treatment and while participating in the trial. Examples of live vaccines include, but are not limited to, the following: measles, mumps, rubella, varicella/zoster, yellow fever, rabies, BCG, and typhoid vaccine.
- Systemic glucocorticoids for any purpose other than to modulate symptoms from an event of clinical interest of suspected immunologic etiology. The use of physiologic doses of corticosteroids may be approved after consultation with the Investigator.

Subjects who, in the assessment by the investigator, require the use of any of the aforementioned treatments for clinical management should be removed from the trial. Subjects may receive other medications that the investigator deems to be medically necessary.

The Exclusion Criteria describes other medications which are prohibited in this trial.

There are no prohibited therapies during the Post-Treatment Follow-up Phase.

